2.4 Diagnostic Agent

Ga-68 DOTATOC has been officially added to MMC's formulary lists having been cleared by both the Radiology and MMC's Pharmacy and Therapeutics committees, the radiation safety committees as well as the NYC Bureau of Radiological Health. Its use as investigational new agent is now possible pending clearance from the institution's regulatory committees for clinical trials.

The chemistry, manufacturing and controls (CMC) for the study agent are described in the Quality module included with the IND submission (appendix a). The following sections are a brief overview of the product.

2.5 Chemical Identity:

The proposed study medication is "Gallium" (⁶⁸Ga)-DOTATOC, where ⁶⁸Ga (the tracer) is a positron-emitter, Octreotide (the peptide) is a somatostatin analogue, and DOTA (chelator) is a chemical chelator used to link ⁶⁸Ga to Octreotide.

Chemical name of Octreotide: L-Cysteinamide,N-[[4,7,10-tris(carboxymethyl)-1,4,7,10-tetraazacyclododec-1-yl]acetyl]-D-phenylalanyl-L-cysteinyl-L-tyrosyl-D-tryptophyl-L-lysyl-L-threonyl-N-[(1R,2R)-2-hydroxy-1-(hydroxymethyl)propyl]-, cyclic (2→7)-disulfide

Molecular weight: 1421.6g/mol (DOTATOC).

Route of administration: intravenous route.

Composition: Each batch preparation of ⁶⁸Ga-DOTATOC contains the following

⁶⁸ Gallium	10-45 mCi in 4 mL	Drug Substance
		precursor

DOTATOC in 0.25 M	50 ± 5 μg in 1.2 mL	Drug Substance
Acetate buffer(pH=5.5)		precursor
Sterile Water for injection	7.4 ± 1 mL	Excipient
Phosphate buffer solution	0.4 ± 0.1 mL	Excipient

⁶⁸Gallium is a short-lived (half-life: 68min) positron-emitting isotope generated from decay of the parent isotope ⁶⁸Germanium (half-life: 271 days) in a ⁶⁸Ga-generator. ⁶⁸Ga decays by electron capture to form Zinc (⁶⁸Zn), which is a stable nuclide. The main advantage of ⁶⁸Ga-generator is its cyclotron-independent availability, which is important for smaller hospitals by providing less expensive and convenient alternative to cyclotron-generated isotopes. Furthermore, the non-halogenated and non-volatile chemical properties of ⁶⁸Ga make this isotope ideal as PET tracer. Other key radiochemical characteristics of ⁶⁸Ga are summarised in the table below.

⁶⁸ Ga physical half-life T½	Decay product	Maximum positron energy	Maximum linear range	Medium linear range
68min	⁶⁸ Zn	1.89MeV	9.1mm	1.9mm

A new ⁶⁸Ga/⁶⁸Ge generator will be fully dedicated to this IND approved clinical investigation.

2.6 Production of ⁶⁸Ga-DOTATOC:

Due to its short half-life (68min), on-site generation of ⁶⁸Ga-labelled radiopharmaceuticals is mandatory. Generation is relatively simple, consisting of the ⁶⁸Ga/⁶⁸Ge-generator being eluted initially with hydrochloric acid. The eluate is submitted to a peptide buffer solution for labeling.

⁶⁸Ga-DOTATOC is labeled according to Current Good Manufacturing Practice (cGMP) per U.S. Food and Drug Administration (FDA) guidelines. Production will be performed at the cGMP suite of [name]. After sterile filtration of the reaction mixture, the product undergoes radiopharmaceutical quality control.

The quality control of the 68Ga-DOTATOC injection solution will be performed by NCM USA Bronx, LLC [name] [contact] [contact]. Appearance, volume, yield, radiochemical purity -HPLC, radioactivity measurements, filter integrity, pH, residual solvent testing, radionuclide identity, radionuclide purity and endotoxin. These tests will be performed before product release, and test results will be documented on the Certificate of Analysis. Additional QC steps, including sterility testing, and Germanium breakthrough. These tests will be performed after product release, and the test results will be included on the Certificate of Analysis.

The Drug Product Ga-68-DOTATOC Injection Solution contains Ga-68-DOTATOC as Drug substance (API) filled in a 25 mL glass vial, closed with a coated (FluoroTec[™]) butyl rubber stopper secured with an aluminum crimp seal. The bottle is shipped from the NCM LLC to the site of administration in a box with lead shielding.

3.0 Inclusion Criteria

- 3.1 Signed informed consent.
- 3.2 Patients of either gender, aged ≥18 years.
- 3.3 Karnofsky status ≥60.
- 3.4 Life expectancy of at least 12 weeks.
- 3.5 Histologically and/or clinically confirmed and/or suspicious of NET.
- 3.6 A diagnostic CT or MRI of the tumour region or suspected area within the previous 4-6 months prior to dosing day is available.
- 3.7 Recent Blood test results up to 4-6 weeks as follows:
 - 3.7.1 WBC: >2*109/L
 - 3.7.2 Haemoglobin: >8.0g/DI
 - 3.7.3 Platelets: >50x10⁹/L
 - 3.87.4 ALT, AST, AP: ≤5 times ULN
 - 3.7.5 Bilirubin: ≤3 times ULN
- 3.8 Serum creatinine: within normal range or <120µmol/L for patients aged 60 years or older.
- 3.9 Negative pregnancy test in women capable of child-bearing.

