5.1.1 PET imaging

⁶⁸Ga-DOTATOC PET images will be acquired 90 ±30 minutes after injection of 111–185 MBq (3-5 mCi) ±25% of ⁶⁸Ga-DOTATOC. Any adverse effects will be documented after the injection of ⁶⁸Ga-DOTATOC. Imaging will be performed with patients in supine position using the Philips Gemini TF time-of-flight (TOF) PET/CT scanner (Philips Medical Systems, Cleveland, Ohio) with a spatial resolution of 5 mm in the center of the field of view, with emission scan acquired for 1 min 40 sec. per frame in 3D acquisition mode. Proprietary vendor-provided software will be used for image reconstruction with LISTMODE OS-EM reconstruction algorithm (33 subsets, 3 iterations). The low-dose CT (LDCT) scan will be used for non-uniform attenuation correction. Both scatter and random corrections will be performed by embedded program provided by the vendor.

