5.1.2 CT Scan

CT scan will be performed using the CT exposure factors for all examinations of 140 kVp and 80-100 mA in 0.8 s. With patient position maintained, a whole-body PET emission scan will be performed covering an area identical to that covered by CT; scans will be performed in 3-dimensional mode. All PET acquisitions will be carried out in 3-dimensional mode (5 min per bed position), in an approximately 40-min scanning time. PET images will be reconstructed using CT for attenuation correction and using ordered-subsets expectation maximization with 2 iterations and 24 subsets.

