5.1.3 PET/CT Images

The images from ⁶⁸Ga-DOTATOC PET/CT will be reported by experienced nuclear medicine physicians. Areas of abnormal focal uptake will be documented. These areas of abnormal uptake will be compared with any prior cross-sectional imaging (CT or MRI) within 12 weeks to confirm the presence of lesions.

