5.2. Interpretation of Data

The number of lesions that could be identified clearly as single focus will be determined for each patient. To enable a methodic and consistent approach to lesion identification, we will create 3 categories of lesion sites: organs (Head and Neck, lungs, breast, liver, pancreas, gastrointestinal tract, kidney, spleen, and pelvis/ovaries), nodal regions (Axillary, thoracic, mesenteric, abdominal, and pelvic [excluding mesenteric], and inguinal regions), and musculoskeletal system (vertebrae, bony thorax, bony pelvis, and limb bones). Because of confluence and inability to clearly delineate single liver lesions in some cases, liver metastases will be classified as 1 organ metastasis, independent of the number of liver metastases present. Lymph nodes smaller than 1 cm on CT or MRI and showing marked avidity for ⁶⁸Ga-DOTATOC will be labeled as positive for

disease. In cases where images from ¹¹¹In-Octreotide are available for comparison, the same imaging parameters will be applied. The presence of lesions will be confirmed by cross-sectional imaging of all patients with CT or MRI. As there may be lesion/s that can show abnormal focal activity on Ga-68 PET images but not on morphologic images, such lesion/s will be considered positive NET.

Each scan (⁶⁸Ga-DOTATOC) will be read by two independent, board certified nuclear medicine physicians blinded to the results of other scan. A third independent nuclear medicine physician will then review both the results (independent reviews) and clinical information to reach to a consensus.

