5.4 Statistical Analysis

The primary goal of the analysis is to estimate the diagnostic accuracy of 68Ga-DOTATOC PET-CT for detecting NET compared to conventional imaging techniques. Analyses will be performed with both patient and lesion as the unit of observation. Since all patients are expected to have at least one NET lesion, only sensitivity can be estimated in the analysis by patient, whereas both sensitivity and specificity will be estimated in the lesion based analysis. We will compute the relevant proportions and corresponding 95% confidence intervals, with adjustment for correlated data from the same patient. Results from pathology reports available from previous biopsy or surgical specimens will be considered the gold standard. In the absence of pathology reports, initial and follow up diagnostic CT or MRI scan following nonsurgical therapy including chemotherapy will be considered the gold standard.

Kappa statistics will be computed and McNemar's test will be performed to compare the sensitivity and specificity between ⁶⁸Ga-DOTATOC PET-CT with SPECT and diagnostic CT for detecting NET. All analyses will be performed in SAS and p-values < 0.05 will be considered statistically significant.

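### The qualifying CT/MRI need cover only the tumour region, yet whole-body PET is compared with it across body-wide lesion sites, with no rule for sites the comparator did not image

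*Combined protocol and SAP*

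**What the plan says.** - **Comparator coverage.** Section 3.0, criterion 3.6, requires: "A diagnostic CT or MRI of the tumour region or suspected area within the previous 4-6 months prior to dosing day is available". Nowhere does the plan require a wider conventional scan or one matched to the PET field.
- **PET coverage.** Section 5.1.2: "a whole-body PET emission scan will be performed covering an area identical to that covered by CT". The CT meant there is the one acquired with the PET. Section 5.1.1 gives its role: "The low-dose CT (LDCT) scan will be used for non-uniform attenuation correction".
- **Sites counted.** Section 5.2 lists "organs (Head and Neck, lungs, breast, liver, pancreas, gastrointestinal tract, kidney, spleen, and pelvis/ovaries", then nodal regions from axillary to inguinal, then the skeleton including limb bones.
- **Confirmation.** Under section 5.1.3, PET foci are "compared with any prior cross-sectional imaging (CT or MRI) within 12 weeks to confirm the presence of lesions". Section 5.2 adds: "The presence of lesions will be confirmed by cross-sectional imaging of all patients with CT or MRI". Neither sets a field of view.
- **Unmatched foci.** Section 5.2, on lesions with "focal activity on Ga-68 PET images but not on morphologic images, such lesion/s will be considered positive NET".
- **Reference and test.** Section 5.4 (Statistical Analysis) takes pathology as the gold standard or, failing that, initial and follow-up diagnostic CT or MRI. Kappa and McNemar's test then compare "PET-CT with SPECT and diagnostic CT for detecting NET". There is no restriction to sites imaged by both tests and no category for a site that was not imaged.

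**The concern.** Suppose a patient qualifies on an abdominal CT and PET shows an avid rib or neck focus. The comparator never looked there. If the rule for unmatched foci in section 5.2 is applied as worded, the focus is a NET lesion, PET found it and CT did not, so it adds a discordant pair in PET's favour. If the CT/MRI reference in section 5.4 is applied instead, the focus has no truth status unless follow-up imaging happens to cover it. In neither case does the score say how well CT detects a lesion it imaged.

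The main objective is accuracy relative to conventional imaging. In the sensitivity comparison this mechanism works in one direction only, and recruiting more patients does not remove it. The same question arises for SPECT wherever an available In-111 study did not cover a site. Unless coverage is recorded as the study runs, it may be hard to recover at analysis.

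**Working it through.** **1. The plan's own figures.** Section 5.4 (Justification of Sample Size) gives 40 patients and 80 lesions, 60% positive: 0.60 × 80 = 48 positive and 32 negative. The worst-case 95% half-width is 1.96 × √(0.25/n):
- n = 48: 14.1% (stated 14%)
- n = 32: 17.3% (stated 17%)
- n = 40: 15.5% (stated 15%)

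These agree to within about half a percentage point. They describe the precision of PET alone and do not bear on the paired comparison.

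**2. Model for the comparison.** From the plan: 48 NET lesions and a 0.05 significance level. Assumed: both tests 80% sensitive within the CT/MRI field, in-field reads independent, lesions independent, a share f of NET lesions outside the field, and every such lesion PET-positive. The last assumption follows from the section 5.2 route, because these lesions enter the count only when PET shows them.

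- In-field discordance in each direction: d = 0.8 × 0.2 = 0.16
- P(PET+, CT−): b = (1 − f) × 0.16 + f
- P(PET−, CT+): c = (1 − f) × 0.16
- Counted CT sensitivity: 0.8(1 − f)
- Counted PET sensitivity: 0.8(1 − f) + f

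Example, f = 20%: c = 0.8 × 0.16 = 0.128 and b = 0.128 + 0.20 = 0.328. CT is counted at 64% and PET at 84%, although the two are equal in field.

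The chance that a two-sided exact McNemar test gives p < 0.05 in PET's favour, by enumeration over 48 lesions:

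| f | CT counted | PET counted | False result for PET |
|---|---|---|---|
| 0 | 80% | 80% | about 1% |
| 5% | 76% | 81% | about 5% |
| 10% | 72% | 82% | about 14% |
| 20% | 64% | 84% | about 46% |
| 30% | 56% | 86% | about 80% |

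**3. Check with rounded expected counts.**
- f = 10%: 5 lesions out of field, 43 × 0.16 ≈ 7 discordant each way, so 12 against 7, p = 0.36.
- f = 20%: 10 out, 38 × 0.16 ≈ 6, so 16 against 6, p = 0.05.
- f = 30%: 14 out, 34 × 0.16 ≈ 5, so 19 against 5, p = 0.007.

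**4. Variation in the assumptions.** If PET finds only 80% of out-of-field lesions, then b = (1 − f) × 0.16 + 0.8f, and the chances at f = 5%, 10%, 20% and 30% are about 4%, 10%, 33% and 63%. With the same 80% and half the in-field discordance (d = 0.08), they are about 13%, 46% and 79% at f = 10%, 20% and 30%.

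**5. Patient level.** Criterion 3.6 requires the scan to cover the tumour or suspected area. A patient with an in-field lesion can be positive on both tests whatever lies elsewhere, so this analysis is affected mainly in patients with no in-field lesion.

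**The case against.** The strongest reply is that the plan is silent rather than wrong. A reader might infer that it instructs the analyst to score an unimaged site as CT-negative. No section says so, and the section 5.2 rule can be read as covering only sites that were imaged and showed nothing. That stands: the defect is a missing rule whose literal reading produces the bias.

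A reader might also infer that an out-of-field focus can never be confirmed. The documents do not support that. Criterion 3.6 is an entry minimum, section 5.2 promises CT or MRI confirmation in all patients, and the section 5.4 reference includes follow-up imaging. Any of these scans may be wider. None is required to be.

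The CT acquired with the PET does cover the same area, so some morphologic image exists. But it is described as low-dose and for attenuation correction, it belongs to the index test, and it is not named as the diagnostic CT comparator. It softens the point without closing it.

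The issue is also partly tied to the truth rule: an unbiopsied out-of-field focus is a true positive only through the section 5.2 rule. Lesions proven by pathology or by later CT/MRI raise the coverage problem whichever rule applies.

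Finally, wider coverage is a real property of PET if conventional imaging means the work-up as performed. That is a legitimate quantity to report, but it should be labelled as coverage and kept apart from detection at sites both tests imaged.

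**Conclusion.** The gap is real and lies in the primary comparison: regional comparator coverage, body-wide lesion counting, a rule that does not separate negative from not imaged, and a McNemar test not limited to co-imaged sites. The direction in the sensitivity comparison is toward PET.

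The size is not established. A reader might take the upper end of the table as the expected harm, but nothing in the documents places f at 10–30%. At f = 5% the false-positive chance is about 5%, against about 1% at f = 0. The figures also treat lesions as independent, whereas section 5.4 expects correlation within patients and plans an adjustment for the proportions and intervals.

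This should be fixed, with moderate confidence. It does not depend on the different scan-age windows in criterion 3.6 (4–6 months) and section 5.1.3 (12 weeks), which need reconciling separately.

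**What to change.** - **Section 5.2.** For each patient, record which of the listed organ, nodal and skeletal sites were covered by the qualifying CT/MRI, by any follow-up CT/MRI and by any In-111 scan. Score uncovered sites as not imaged, never as negative.
- **Section 5.4 (Statistical Analysis).** Make the paired sensitivity, specificity, kappa and McNemar comparisons on sites imaged by both tests. Report PET foci outside the comparator's field separately and descriptively. An all-sites analysis may be shown as secondary, labelled as reflecting coverage.

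**Cost.** One case report form field per site and a short addition to the analysis text, with no new scans. The paired set shrinks: at f = 10% to 30%, 43 to 34 of the 48 NET lesions remain. The worst-case sensitivity half-width becomes 1.96 × √(0.25/43) = 14.9% to 1.96 × √(0.25/34) = 16.8%, instead of 14.1%. The apparent advantage of PET will probably be smaller.

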4.0 Exclusion Criteria

- 4.1 Known hypersensitivity to DOTA, to ⁶⁸Gallium, to DOTATOC or to any of the excipients of ⁶⁸Ga-DOTATOC.
- 4.2 Therapeutic use of any somatostatin analogue, including Sandostatin® LAR (within 21 days) and Sandostatin® (within 2 days) prior to study imaging. It can be stopped for shorter period, depending on the PIs discretion.
- 4.3 Pregnant or breast-feeding women.
- 4.4 Current somatic or psychiatric disease/condition that may interfere with the objectives and assessments of the study.

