5.0 Study design

This is a prospective, Phase 2, single center study in a total of 40 subjects with Neuroendocrine Tumors (NETs). Study participants will receive 68Ga-DOTATOC and undergo a PET/CT imaging study, to investigate its suitability as a PET imaging agent for NETs. The radiation (imaging) dose will be $111-185 \, \text{MBq} (3 - 5 \, \text{mCi}) \pm 25\%$. All doses after labeling will be presented in buffered solution for intravenous injection. Imaging will start 90 $\pm 30 \, \text{minutes}$ after injection.

About 40 patients with histologically and/or clinically confirmed and/or suspected NET are anticipated to be enrolled during 3 years from initiating the study.

Patients will be recruited at Montefiore Medical Park where there is a medical group specialised in the diagnosis and treatment of NETs. Each patient will undergo a screening visit within 14 days prior to receiving study medication.

The primary goal of the analysis is to estimate the diagnostic accuracy of 68Ga-DOTATOC PET-CT for detecting NET compared to conventional imaging techniques.

The patients will be followed up by a telephone call 24 hour after administration of test drug (⁶⁸Ga-DOTATOC) to assess if patients have experienced any adverse event. This information will be captured in the CRF for further assessment.

5.1 Image Acquisition:

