5.4 Justification of Sample Size

We project that it will be feasible to recruit a total of 40 patients with histologically and/or clinically confirmed and/or suspected NET into the study. Each subject is expected to have on average 2 lesions and among the 80 total lesions; we project that 60% will be positive for NET. To evaluate the adequacy of the sample size (i.e., number of lesions), we computed the precision, as measured by the width of the 95% CI, with which the sensitivity and specificity of 68Ga-DOTATOC PET-CT scan can be estimated. The width of the 95% CI will be no greater than +/-14% for sensitivity and +/- 17% for specificity in the lesion-based analysis. For the patient-based analysis, the precision with which sensitivity can be estimated is +/- 15%.

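### The analogue-withdrawal rule covers the study PET but not the archived In-111 SPECT it is tested against, so the PET-versus-SPECT difference may partly reflect drug status

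*Combined protocol and SAP*

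**What the plan says.** Exclusion criterion 4.2 (section 4.0) rules out "Therapeutic use of any somatostatin analogue, including Sandostatin® LAR (within 21 days) and Sandostatin® (within 2 days) prior to study imaging". It then adds: "It can be stopped for shorter period, depending on the PIs discretion".

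Section 5.0 defines what the study performs: "Study participants will receive 68Ga-DOTATOC and undergo a PET/CT imaging study, to investigate its suitability as a PET imaging agent for NETs". No In-111 scan is scheduled anywhere in the protocol.

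Section 5.2 brings in the SPECT comparator: "In cases where images from ¹¹¹In-Octreotide are available for comparison, the same imaging parameters will be applied". It sets no limit on the date of that scan and no condition on treatment at the time.

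Section 5.4 (Statistical Analysis) states that "McNemar's test will be performed to compare the sensitivity and specificity between ⁶⁸Ga-DOTATOC PET-CT with SPECT and diagnostic CT for detecting NET", and that "All analyses will be performed in SAS and p-values < 0.05 will be considered statistically significant". It plans no restriction, stratification or sensitivity analysis by analogue exposure. Section 5.3 collects demographics and patient-reported medical history. It does not ask for analogue dates relative to either scan.

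**The concern.** The background (section 2.0) explains that both agents image by binding somatostatin receptors and that the gallium agent carries the same analogue as In-111 octreotide. It also lists somatostatin analogues among the usual NET medicines. If recent analogue treatment matters enough to exclude a patient before the PET, it is relevant to the SPECT as well.

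As written, a patient could have had the In-111 scan while on a long-acting analogue, stopped the drug to qualify, and then had the PET. That pair enters McNemar's test as off-drug PET against on-drug SPECT. The test sees only which scan found the disease. It cannot separate tracer and camera from drug status. The sentence in 5.2 about applying the same parameters cannot alter the treatment a patient was on at a scan already acquired.

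Comparison with conventional imaging is part of the stated primary goal, and SPECT is one of the two named comparators. At stake is whether a PET-versus-SPECT difference can be read as a property of the tracer. The question is separate from the age of the SPECT: it arises even when the two scans are close together.

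**Working it through.** **1. The plan's own figures.** The documents give no power or effect size for PET versus SPECT. They give only precision for PET alone, from 40 patients and 80 lesions, 60% positive (48 positive, 32 negative). The half-width is 1.96 × √(0.25/n):
- n = 48: 14.1% (plan: 14%)
- n = 32: 17.3% (plan: 17%)
- n = 40: 15.5% (plan: 15%)

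These reproduce to within rounding down. They do not involve SPECT, so this point leaves them untouched.

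**2. Form of the bias.** Let f_S be the share of SPECT scans done on analogue and d_S the loss of SPECT sensitivity in those scans, with f_P and d_P the same for PET. Then

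shift in (PET − SPECT sensitivity) = f_S·d_S − f_P·d_P.

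Criterion 4.2 pushes f_P down but, because of the discretion clause, not necessarily to zero. Nothing constrains f_S. None of the four quantities is in the documents.

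**3. Range under assumptions, with f_P = 0.** Assume equal off-drug sensitivity s = 0.90, independent errors and independent pairs. SPECT sensitivity becomes s₂ = s − f_S·d_S. The chance that only PET is positive is s(1 − s₂), and that only SPECT is positive (1 − s)s₂. For f_S = 0.5 and d_S = 0.2: s₂ = 0.80, giving 0.18 and 0.08, a difference of 0.10. Chance of a significant result favouring PET, uncorrected McNemar (exact test in brackets):

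| f_S, d_S | shift (points) | 40 pairs | 20 pairs |
|---|---|---|---|
| 0 | 0 | 2.3% (0.8%) | 2.0% (0.2%) |
| 0.25, 0.1 | 2.5 | 4.7% (2.2%) | 3.8% (0.5%) |
| 0.5, 0.2 | 10 | 21.2% (14.6%) | 12.8% (4.1%) |
| 0.5, 0.4 | 20 | 59.9% (50.5%) | 32.4% (18.8%) |

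With small f_S·d_S the effect is minor; with large values it is not. The two columns are illustrations: 40 pairs would require every patient to have a SPECT. Several lesions from one patient are correlated, which adds uncertainty not shown here.

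**4. How few discordant pairs matter.** With b pairs in PET's favour and none the other way, the uncorrected chi-square equals b and the exact two-sided p is 2 × 0.5^b. For b = 4, p = 0.046 (uncorrected). For b = 5, exact p = 0.0625. For b = 6, exact p = 0.031.

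**5. What the protocol leads one to expect anyway.** In the cited 84-patient study (section 2.3), PET was true positive in 69 and false negative in 2; SPECT was true positive in 37 and false negative in 34. Among 71 patients with disease, that is 69/71 = 97% against 37/71 = 52%. The 32 patients positive on PET and missed on SPECT account for the whole difference (69 − 37 = 32), so none went the other way. The discordance rate is 32/71 = 45%. At that rate, the chance of 6 or more such pairs is 94.5% with 20 pairs and above 99.9% with 40.

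**The case against.** The strongest reply is that the mechanism is inferred. Criterion 4.2 gives windows without a reason, and no section says that analogues block uptake or by how much. One cited study withheld long-acting analogues before follow-up imaging, again with no reason given. This stands as a limit on size. It does not remove the asymmetry, which is in the text.

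Second, the direction is not fixed, because the discretion clause allows some PETs to be done after a shortened interval. This stands too. It does not align the two scans; it leaves both uncontrolled.

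Third, a reader might infer from step 4 that drug effect in 4 to 6 of 40 patients (10% to 15%) could by itself create a significant PET advantage. The documents do not support that:
- SPECT is used only where it exists, so 40 is not the number of pairs.
- A patient-level miss requires every lesion SPECT would have shown to be lost while PET still finds one.
- The supposition of no other discordance conflicts with the 84-patient study, on whose figures significance is likely regardless. The protocol's summary does not give analogue status at those scans, so that study cannot measure the drug effect either.

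Fourth, this is one facet of a loosely specified SPECT comparator, and a single definition could cover it along with scan age. That is a fair point about drafting, but a date limit alone would not settle analogue status.

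**Conclusion.** The concern holds in a limited form. The plan applies an analogue condition to one of two paired receptor-imaging tests and then compares them formally. A difference in drug status can therefore be mixed into the PET-versus-SPECT contrast, and nothing in the plan would let an analyst detect it afterwards.

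The supportable claim is that the difference may be inflated in PET's favour where patients were on analogue at the SPECT and off it at the PET, with a possible bias the other way where the PET interval was shortened. The documents do not support a claim that the asymmetry creates the result, or that it certainly favours PET.

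The size is unknown. The assumed range of 2.5 to 20 points rests on f_S, d_S and f_P = 0, none of which is documented. The diagnostic CT comparison, PET's own sensitivity and specificity, and the sample-size precision are unaffected. This should be corrected before analysis, but it does not undermine the study as a whole.

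**What to change.** In sections 5.2 and 5.4:
- From existing medical records, capture for both the PET and the In-111 scan the analogue name, date of last dose and days from last dose to scan. State how many patients have a SPECT at all.
- Report the PET-versus-SPECT McNemar result for pairs in which the 4.2 condition was met at both scans, beside the result for all available pairs. Give the discordant counts in each direction for both.
- State in advance that the all-pairs difference will not be attributed to the tracer unless the matched-status result agrees.
- Class pairs with unknown analogue status as unmatched, and show their number.

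Reporting both results is preferable to barring unmatched scans from the formal test. Exclusion would shrink a subset of unknown size and select against patients treated with analogues.

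The cost is a medication-record check for each patient with a SPECT, and a matched analysis with fewer pairs and wider intervals. The sponsor should also reconcile the fixed windows in 4.2 with its discretion clause, so that the matching condition is defined. No washout length is proposed here.
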